9.4 Treatment Compliance

Table 6: Treatment Compliance Measures

Characteristic [mean ± SD or n (%)]	All n=	Expanded Intervention n =	Brief Intervention n =
Average number of Intervention sessions completed			
Percentage of participants completing 60% of Intervention sessions			

10 Efficacy Analyses

The primary and secondary outcomes will be summarized stratified by treatment group at each study timepoint (baseline, 12-week, 24-week). Our primary analysis will use an intention-to-treat (ITT) analysis that includes all participants who wore the monitor for \geq 4 days for 10 hours/day at baseline. The statistical model underlying the analysis a mixed-effects model to examine the main and interaction effects of *group* (Expanded Intervention

vs. Brief Intervention) and *time* (BL, 12-week) on MVPA (minutes/day). The null hypothesis is that there is no difference in change in MVPA in the Expanded Intervention group compared to the Brief Intervention group. The alternative hypothesis is that there is a difference between groups. The nature of the hypothesis is confirmatory as this study has been powered to detect a difference should one exist. The mixed-effect model will be used to calculate the mean and 95% Confidence Interval time in MVPA at each study time point. We will also calculate the difference in means and 95% Confidence Intervals between the Expanded Intervention and Brief Intervention group at each study time point. We will also calculate 2-sided p-values to determine statistical significance of differences between groups by time in MVPA. Data will be summarized by intervention group. Means, Standard Deviations, Minimums and Maximums will be used to summarize continuous variables. Categorical variables will be summarized as frequencies and percentages.

Mixed-effect modeling will be used to estimate MVPA over time. The mixed-effect model using restricted maximum likelihood estimation is a full information approach and leads to unbiased model parameter estimates in the presence of MCAR or MAR missingness. Selection between models with two common covariance structures, Toeplitz and independent errors, will be accomplished using the Akaike Information Criterion (AIC).

10.1 Primary Efficacy Analysis

The primary endpoint of our study is to examine the efficacy of a physical therapist-delivered exercise intervention (Delaware PEAK, referred to as the Expanded Intervention) to increase MVPA over 12 weeks compared to a control group receiving web-based resources about knee OA and exercise (referred to as the Brief Intervention).

The statistical model underlying this analysis is a mixed-effects model to examine the main and interaction effects of *group* (Expanded Intervention vs. Brief Intervention) and *time* (baseline, 12-week) on MVPA (minutes/day).

10.2 Secondary Efficacy Analyses

10.2.1 Secondary Analyses of Primary Efficacy Endpoint

The per protocol samples, instead of the ITT sample will be used for the analysis of the primary efficacy endpoint.

10.2.2 Analyses of Secondary Endpoints

The secondary analyses endpoints are to examine the efficacy of a physical therapistdelivered exercise intervention (Delaware PEAK, referred to as the Expanded Intervention) to increase treatment beliefs, increase LPA, and increase steps/day over 12 weeks compared to a control group receiving web-based resources about knee OA and exercise (referred to as the Brief Intervention). Additionally, we will examine the efficacy of the intervention to increase MVPA over 24 weeks.

10.3 Exploratory Efficacy Analyses

Further, we will explore the efficacy of a physical therapist-delivered exercise intervention (Delaware PEAK, referred to as the Expanded Intervention) to decrease VAS pain and increase KOOS subscale scores over 12 weeks compared to a control group receiving webbased resources about knee OA and exercise (referred to as the Brief Intervention). We also will explore the change in exercise adherence from the 12-week to 24-week follow-up timepoints in the Expanded Intervention group only. Lastly, we will examine changes in treatment expectations between group from before to after randomization.

11 Safety Analyses

- All-Cause Mortality: A table of all anticipated and unanticipated deaths due to any cause, with frequencies and percentages of such events in each Intervention group will be reported.
- Serious Adverse Events: A table of all anticipated and unanticipated serious adverse events, grouped by organ system, with frequencies and percentages of such events in each Intervention group will be reported.
- Other (Not Including Serious) Adverse Events: A table of anticipated and unanticipated events (not included in the serious adverse event table) that exceed a frequency threshold of 5% within either Intervention group, grouped by organ system, with frequencies and percentages of such events in each Intervention group will be reported.

11.1 Adverse Events

We will report on the frequencies and percentages of adverse events that are possibly or definitely related to the study.

11.2 Deaths, Serious Adverse Events and other Significant Adverse Events

We will report on the frequencies and percentages of deaths, serious adverse events, and other significant adverse events that are possibly or definitely related to the study.

12 Reporting Conventions

P-values ≥ 0.01 will be reported to 3 decimal places; p-values less than 0.001 will be reported as "<0.001". The mean, standard deviation, and any other statistics other than quantiles, will be reported to one decimal place greater than the original data. Quantiles, such as median, or minimum and maximum will be reported to one decimal place.

13 Quality Assurance of Statistical Programming (As Applicable)

At the time of this writing, data will be stored on REDCap, a password-protected 2-factor authentication, data management platform hosted by the Center for Human Research Coordination at the University of Delaware.

At the time of this writing, data analysis will be performed using JMP, Version 17.0.0. SAS Institute Inc., Cary, NC, USA.

For quality assurance, all summary score calculations will be performed by REDCap software and checked by a research assistant for accuracy.

14 Summary of Changes to the Protocol and/or SAP

Rationale for Adjustments of Statistical Analysis Plan from Protocol (March 12, 2023) The changes from the protocol-specified definitions of aims, outcomes and statistical analytic approaches are outlined below. These changes reflect an error in data collection during the trial. Questionnaires are collected via automated survey in REDCap, and the automated survey did not include the SEE for the 12-week and 24-week follow-up timepoints. Therefore, SEE was only collected at the baseline timepoint and cannot be assessed for change after the intervention.

15 References


16 Listing of Tables, Listings and Figures

This section is to give precise details for each table, listing or figure to be produced.

Mock Table 1: MVPA at each study time point using the ITT sample

	Baseline	12-week	24-week
Brief Intervention			
Expanded Intervention			
Brief-Expanded			

Mock Table 2: TOA-PT at each study time point using the ITT sample

	Baseline	12-week	24-week
Brief Intervention			
Expanded Intervention			
Brief-Expanded			

Mock Table 3: TOA-PE at each study time point using the ITT sample

	Baseline	12-week	24-week
Brief Intervention			
Expanded Intervention			
Brief-Expanded			

Mock Table 4: Steps/day at each study time point using the ITT sample

	Baseline	12-week	24-week
Brief Intervention			
Expanded Intervention			
Brief-Expanded			

SAP version 1.0: Delaware PEAK

Mock Table 5: VAS Pain at each study time point using the ITT sample

	Baseline	12-week	24-week
Brief Intervention			
Expanded Intervention			
Brief-Expanded			

Mock Table 6: KOOS at each study time point using the ITT sample

	Baseline	12-week	24-week
Brief Intervention			
Expanded Intervention			
Brief-Expanded			

Mock Table 7: MVPA at each study time point using the per-protocol sample

	Baseline	12-week	24-week
Brief Intervention			
Expanded Intervention			
Brief-Expanded			

Mock Table 8: TOA-PT at each study time point using the per-protocol sample

	Baseline	12-week	24-week
Brief Intervention			
Expanded Intervention			
Brief-Expanded			

Mock Table 9: TOA-PE at each study time point using the per-protocol sample

	Baseline	12-week	24-week
Brief Intervention			
Expanded Intervention			
Brief-Expanded			

Mock Table 10: Steps/day at each study time point using the per-protocol sample

	Baseline	12-week	24-week
Brief Intervention			
Expanded Intervention			
Brief-Expanded			

Mock Table 11: VAS Pain at each study time point using the per-protocol sample

	Baseline	12-week	24-week
Brief Intervention			
Expanded Intervention			
Brief-Expanded			

SAP version 1.0: Delaware PEAK

Mock Table 12: KOOS at each study time point using the per-protocol sample

	Baseline	12-week	24-week
Brief Intervention			
Expanded Intervention			
Brief-Expanded

### Sponsor: University of Delaware

## Funded by: Rheumatology Research Foundation

### Date of SAP: 4/5/2024

Version	Date	Summary of changes	
v0.01	07/14/2023	Original	
v0.02	8/7/2023	Clarified analysis section 8.2.1 and 8.2.2	
v0.03	8/16/2023	Revised section 6.4 and clarified section 8.2.1 and 8.2.2	
V1.00	9/25/2023	Revised section 8.2.1 to clarify the ITT sample would include only those with complete baseline monitor data. Added a 24 week follow up to analyses described in sections 10.2.2 and 10.3	
V1.1	12/19/2023	Revised the study flow chart and the per protocol sample sets 1 and 2 to a single per protocol sample. Clarified that valid ActiGraph data includes those who wore the monitor for $\geq$ 4 days in section 6.4 instead of in section 8.2. Clarified an index knee for VAS Pain for analysis. Revised secondary data analysis sample (8.2.3) to only include the per protocol analysis and report on outcomes measured with the ActiGraph. Clarified in 8.2.2 that the per protocol sample is a subset of the ITT sample. We clarified in section 5.2 that we are examining health beliefs in physical exercise and physical therapy. We added additional exploratory outcomes. We added exploratory measures from section 5.2 into Table 1 in section 6.4 and removed adverse events as these are listed in section 11.1. We clarified that the EARS will be collected at 12 and 24 weeks in section 6.4. We clarified that both the ITT and per protocol samples will be used for analyses for secondary and exploratory outcomes separately in sections 10.2./10.3. Mock tables in section 16 were revised.	
V1.2	7/2/2024	Modified table 5 collapsing urban area and urban cluster. Replaced	

supplemental table 4 for tables 4A and 4B. Renumbered section 9.4 as Efficacy Analysis.
Modified supplemental table 5. Added supplemental table 6. Section 9.3 table 6 modified and added supplemental table 8 to describe treatment fidelity to exercise and education. Added supplementary table 10 for treatment expectations before and after randomization.
Renamed the expanded intervention group as the intervention and the Brief intervention group as the control.

# 3 Abbreviations and Definitions

AE	Adverse Event
CRF	Case Report Form
SAP	Statistical Analysis Plan
PT	Physical Therapy
EARS	Exercise Adherence Rating Scale
MVPA	Moderate-to-Vigorous intensity Physical
	Activity
SED	Sedentary Behaviors
LPA	Light Intensity Physical Activity
NICE	National Institute for Health and Care
	Excellence
IPAQ	International Physical Activity Questionnaire
VAS	Visual analogue scale
CCI	Charlson Comorbidity Index
PEAK	Physical Exercise and Activity for Knee
	osteoarthritis

### 4 Introduction

### 4.1 Preface

**Knee Osteoarthritis (OA) is a serious disease.** In 2010, OA moved up from 15th to 11th in rankings for global burden of disease, and the most common weight-bearing joint affected by OA is the knee. More than 15 million Americans currently have symptomatic knee OA. The estimated annual cost to treat knee OA is \$27 billion, which is similar to the cost to treat stroke (~\$34 billion). The incidence of knee OA is expected to increase with the aging and obese US population. Walking difficulty is the primary functional limitation in people with knee OA that, in turn, makes OA the leading cause of disability among older adults. Not only is walking difficulty related to disability, but it is also associated with a 55% higher risk of premature death. Without a cure, treatment for knee OA focuses primarily on managing pain and reducing disability.

**Treatment guidelines for knee OA champion the use of supervised exercise.** The recently released 2019 ACR/Arthritis Foundation guidelines for the treatment of OA strongly support the use of supervised exercise. These recommendations are consistent with those of the Osteoarthritis Research Society International (OARSI), which promote exercise, self-management, and education. Both guidelines (ACR and OARSI) come from the robust and pervasive research findings that exercise reduces pain and improves physical function in adults with knee OA.

**Few adults with knee OA try supervised exercise to manage their OA.** For example, less than 10% of adults with knee OA exercise regularly, and only one-in-ten patients are seen for supervised exercise 5 years before a knee replacement. Health claims data show a similar trend, with a doubling in the prescription of opioids and a 50% reduction in referrals for Physical Therapy (PT) in the past decade. Hence, few adults with knee OA are utilizing physical activity and/or supervised exercise to address their symptoms of knee OA.

The objective of this study is to examine the efficacy of Delaware PEAK to increase physical activity in adults with knee OA compared to a control group receiving web-based resources about knee OA and exercise. The rationale for our study is that there is a need to examine whether Delaware PEAK can directly target the mismatch between OA recommendations and practice patterns. Our central hypothesis is that Delaware PEAK will increase physical activity and will increase the belief that exercise is helpful and not harmful, compared with a control group receiving web-based OA treatment resources. Successful completion of this proposal will provide the evidence necessary to scale up this low-cost intervention, with the goal of increasing the number of adults who use exercise to manage their knee OA and thus reducing the burden of disease.

### 4.2 Scope of the analyses

These analyses will assess the efficacy of a physical therapist-delivered exercise intervention (Delaware PEAK) versus a control group receiving web-based resources about knee OA and exercise regarding change in Moderate-to-Vigorous intensity Physical Activity (MVPA) over 12 weeks in adults with knee OA.

# 5 Study Objectives and Endpoints

### 5.1 Study Objectives

The purpose of this study is to examine the efficacy of Delaware PEAK to increase physical activity in adults with knee OA compared to a control group receiving web-based resources about knee OA and exercise.

### 5.2 Endpoints

The primary endpoint of our study is to examine the efficacy of a physical therapist-delivered exercise intervention (Delaware PEAK) to increase MVPA over 12 weeks compared to a control group receiving web-based resources about knee OA and exercise.

The secondary analyses endpoint of our study is to examine the efficacy of a physical therapist-delivered exercise intervention (Delaware PEAK) to increase health beliefs in Physical Exercise and Physical Therapy, light physical activity (LPA), and steps per day, over 24 weeks compared to a control group receiving web-based resources about knee OA and exercise. We also will assess change in MVPA over 24 weeks.

Our exploratory endpoints include change in pain, symptoms, function in activities of daily living, function in sport and recreation, and quality of life over 12 weeks and 24 weeks. We will also examine change in treatment expectations before and after randomization. Lastly, we will examine change in treatment adherence from 12 to 24 weeks among those in the intervention group.

[figure not shown]
# 6 Study Methods

### 6.1 General Study Design and Plan

(ICH E3;9)

We will conduct a pragmatic randomized controlled trial with a 2-group, superiority, paralleldesign. The intervention group will receive a physical therapist-delivered exercise intervention (Delaware PEAK), i.e., the Intervention, while the control group will receive webbased resources about knee OA and exercise. The study was assessor-blinded, i.e., all members of the research team who were involved with the assessment of the primary and secondary outcomes were blinded. Participants will not be blinded to group assignment but will not be informed about study hypotheses until study completion. The physical therapist will not be blinded to group assignment.

#### Figure 1: Study flow-chart

### 6.2 Inclusion-Exclusion Criteria and General Study Population

(ICH E3;9.3. ICH E9;2.2.1)

In order to be eligible to participate in this study, an individual must meet all of the following criteria:

- 1. Provision of an electronically signed and dated informed consent form
- 2. >45 years of age,
- 3. Resides in the contiguous United States
- 4. Available for the duration of the intervention portion of the study (12 weeks) and willing to wear physical activity monitors
- 5. Looking to move more, i.e., be more active.
- 6. Knee OA diagnosis by the NICE criteria
- 7. Comfortable participating in a program delivered in English
- 8. Is able to safely participate in moderate-intensity exercise as determined by a preexercise screen questionnaire,
- 9. Has either a smartphone or a laptop/desktop computer with an internet connection.
- 10. Has a working email address.

An individual who meets any of the following criteria will be excluded from participation in this study:

- 1. Regularly exercise for more than 60 minutes/week.
- 2. Has a scheduled knee or hip joint replacement
- 3. Has had physical therapy for knee OA in the past 6 months
- 4. Participated in a strength training program for the lower extremities in the past 6 months

# 6.3 Randomization and Blinding

(ICH E3; 9.4.3, 9.4.6. ICH E9; 2.3.1, 2.3.2)

Participant-level randomization will be performed to assign each participant to either the Intervention group (referred to as the Intervention) or the Control group using block randomization schedule with block sizes of 4. Randomization was performed using REDCap's built-in randomization function and will occur after participants sign the informed consent and complete baseline data collection. Participants will be randomized into one of two groups: (1) the Intervention group, who will receive the Delaware PEAK program with a physical therapist, or (2) the control group, who will receive pre-recorded, web-based resources.

Participants will not be blinded to group allocation; however, they will not be informed about the study hypotheses until the study is completed, at which time they will be provided a lay summary of findings. The treating physical therapist will not be blinded to group assignment, as they are delivering the Intervention. Research team members responsible for outcome data management will be blinded to group assignment. As all outcomes are collected either through a physical activity monitor or online questionnaires, this study is thus considered assessor-blinded for our primary outcome, physical activity. Statistical analyses will be performed in a blinded manner.

### 6.4 Study Assessments

(ICH E3; 9.5.1. ICH E9; 2.2.2)

#### Table 1: Timeline of Assessments

	STUDY PERIOD								
	Enrollment/BL	Randomization		Int	terven	tion		Follo	w-Up
Timepoint	- t 1	0w	lw	2w	4w	7w	10w	12w	24w
Enrollment:									
Screening Form	Х								
Verbal Eligibility Form	Х								
Informed Consent	Х								
General Information (Demographics)	Х								
Randomization		Х							
Intervention:									
Intervention			Х	Х	Х	Х	Х		
Control			Х	Х	Х	Х	Х		
Assessment:									
Primary outcome									
Physical activity (MVPA via Actigraph)	Х							Х	Х
Secondary outcomes									
Treatment Beliefs of Physical Therapy	Х							Х	Х
Treatment Beliefs of Physical Exercise	Х							Х	Х
Physical activity (steps/day, LPA via Actigraph)	Х							Х	Х
Exploratory measures									
Knee Pain (Visual Analogue Scale)	Х							Х	Х
Knee Injury and OA Outcome Score (KOOS) subscales: Pain, Symptoms, function in activities of daily living, function in sport and recreation, quality of life	х							Х	Х
Treatment Expectations Question	Х	Х							
Exercise Adherence Rating Scale (EARS)*								Х	Х
Other measures									
Adverse Events		X	Х	Х	Х	Х	Х	Х	Х
Charlson Comorbidity Index	Х								
*Collected in the those randomized to the intervent	ntion group								

#### Table 2: Analysis Time Windows

Visit (target day)	Lower bound (days)	Upper bound (days)	
Enrollment (0)	n/a	n/a	
Baseline (14, post-enrollment)	n/a	n/a	

12-week Follow-up (84, post-randomization)	-7 days	+28 days
24-week Follow-up (168, post-randomization)	-7 days	+28 days

Data collected outside of the time windows listed above will be classified as the intended visit the data was to reflect and noted as being outside the time window. Such data will be included in the primary analyses, however we will also perform a secondary analyses excluding data collected outside the time window. While the spacing of follow-up assessments makes it unlikely that multiple data collections will occur during the same window, the first valid set of assessments will be used for the corresponding timepoint.

Descriptions of each outcome, timepoint of collection, and score range are described below. A table is also provided that summarizes this information.

**MVPA**: Objectively-measured physical activity will be collected using the Actigraph GT3x at the baseline, 12-week, and 24-week timepoints. Minutes/week of MVPA can range from 0 minutes/week to 10,080 minutes/week (7 days x 24 hours x 60 minutes). Valid data includes those who wore the ActiGraph for  $\geq$  4 days.

*LPA, Daily Walking*: Data collected using the ActiGraph GT3x activity monitor will also be used to assess change in minutes/week of LPA and average steps/day between baseline and both follow-up timepoints. Minutes/week of LPA can range from 0 minutes/week to 10,080 minutes/week (7 days x 24 hours x 60 minutes). Steps/day can be any value greater than or equal to 0. Valid data includes those who wore the ActiGraph for  $\geq$  4 days.

*Health Beliefs*: Health beliefs will be measured with the Treatment Beliefs of OA: Physical Therapy (TOA-PT) and Treatment Beliefs of OA: Physical Exercise (TOA-PE) questionnaires, collected at the baseline, 12-week, and 24-week timepoints. The TOA provides separate scores for positive and negative treatment beliefs. We will measure change in TOA-PT and TOA-PE scores from baseline to 12 weeks and baseline to 24 weeks. The TOA-PT negative beliefs scores range from 4 to 16, TOA-PT positive scores range from 7 to 28, TOA-PE negative beliefs scores range from 4 to 16, TOA-PE positive scores range from 7 to 28. For all scales, a higher score indicates a greater amount of positive or negative treatment beliefs.

*Charlson Comorbidity Index (CCI)*: The Charlson Comorbidity Index (CCI) is a 17-item questionnaire that creates a weighted score based on a range of common, comorbid conditions. This questionnaire will be collected at the baseline timepoint and scores range from 0 to 29, with a higher CCI score indicating greater levels of comorbidity.

*Visual Analog Scale (VAS) Pain*: Change in knee pain will be measured using a single-item Visual Analog Scale (VAS) question in which the participant will indicate their pain in each knee. Scores range from 0-100 where 0 is no pain and 100 is the worst pain imaginable. An index knee to be used for analysis is defined as the knee with worse pain at baseline.

*Knee Injury and Osteoarthritis Outcome Score (KOOS)*: The Knee Injury and Osteoarthritis Outcome Score (KOOS) is a 42-item questionnaire that assesses five domains, including pain, symptoms (other than pain), function in activities of daily living, function in sport and recreation, and quality of life. The KOOS has subscale scores for Pain, Symptoms, ADL Function, Sport & Recreation Function, and Quality of Life. Scores are transformed to a 0-100 scale with 0 indicating extreme knee problems and 100 indicating no knee problems.

**Treatment Expectations Question**: The participant will complete a Treatment Expectations Question, which asks the participant how effective they expect the intervention to be for their knee. This question will be collected at the baseline timepoint: right before and right after randomization. Answers will be expressed as frequencies and percentages for each of the following categories: No effect at all, Minimal improvement, Moderate improvement, Large improvement, and Complete recovery, as well as reported as an increase, decrease, or no change in treatment expectations.

*Exercise Adherence*: For the Intervention, adherence to strengthening exercises and physical activity will be measured using the Exercise Adherence Rating Scale (EARS). The EARS includes 6 items whose total score ranges from 0 to 24, where a higher score indicates greater adherence. The EARS will be collected at 12 and 24 weeks.

*Adverse Events (AE)*: Information on potential adverse events (AE) will be collected by the treating physical therapist at the beginning of each session in the intervention, by a Research Assistant during follow-up reminder phone calls in the Control, or by spontaneous report on the part of the participant (e.g., reaching out to the study team by phone or email). AEs will be reported as frequencies and percentages.

**General Information Form**: The participant will complete a General Information Form that collects height, weight, date of birth, gender, race, ethnicity, veteran status, highest level of education attained, employment status, and approximate household income. This form will be collected at the baseline timepoint. Continuous variables will be expressed as means and standard deviations while categorical variables will be expressed as frequencies and percentages.

Outcome	Timepoints collected	Scoring	
MVPA	Baseline, 12-week, 24-week	0 to 1044 minutes/day	
TOA (PT and PE)	Baseline, 12-week, 24-week	4 to 16 for negative 7 to 28 for positive	
EARS	12-week, 24-week	0 to 24	
Light intensity physical activity (LPA)	Baseline, 12-week, 24-week	0 to 10,080 minutes/week	
Daily Walking (steps/day)	Baseline, 12-week, 24-week	At least 0 steps/day	
VAS Pain	Baseline, 12-week, 24-week	0 to 100	
KOOS Subscales	Baseline, 12-week, 24-week	0 to 100 for each subscale	
General Information Form	Baseline	n/a	
Treatment Expectations	Baseline (x2)	n/a	
ССІ	Baseline	0 to 29	
Exercise Adherence (EARS)	12-week and 24-week	0-24	

Table 3: Outcome Timepoints and Scoring

Adverse Events	Throughout	n/a
----------------	------------	-----

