#### **Treatment Compliance**

#### Table 6: Treatment Compliance Measures

Table 0. Treatment Compliance Measures	Control		
	-	Intervention	
Number of physical therapy consultations (0-5), mean (SD)	_		
Number of physical therapist consultations, n (%)			
0	-		
1	-		
2	-		
3	-		
4	-		
5	-		
Duration of physical therapist consultations (mins), mean (SD)			
Initial	-		
Follow-ups	-		
PT discussed steps/day n/N (%)			
1 st consultation	-		
2 nd consultation	-		
3 rd consultation	-		
4 th consultation	-		
5 th consultation	-		
PT discussed step goals n/N (%)			
1 st consultation	-		
2 nd consultation	-		
3 rd consultation	-		
4 th consultation	-		
5 th consultation	-		
Self-reported adherence to exercises (EARS) 			
12 weeks	-		
24 weeks	-		
Website access, n/N (%)			
Never		-	
> 1 visit		-	

<sup>1 EARS (Exercise Adherence Rating Scale) range 0-24 with higher scores representing more adherence. SAP version 1.2: Delaware PEAK3/1/24 Page 20 of 38

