### Supplemental table 3: Per protocol sample change within and between groups

 <sup>13 MVPA: Moderate to Vigorous Intensity Physical Activity
  Treatment Beliefs of OA: Physical Exercise

<sup>15 Treatment Beliefs of OA: Physical Therapy SAP version 1.2: Delaware PEAK3/1/24

Supplemental table 4A: Secondary Data Analysis Sample (Per protocol sample excluding those who wore the ActiGraph monitors outside of the established visit windows) sample adjusted mean (se)

Outcome [adjusted	Baseline	12 weeks	24 weeks	P value
mean (se)];n				
Primary Outcome				
MVPA  (min/day)				
Secondary Outcomes				
Light Intensity				
Physical Activity				
Steps/day				

Supplemental table 4B: Secondary Data Analysis Sample (Per protocol sample excluding those who wore the ActiGraph monitors outside of the established visit windows) scores for study outcomes across time change within and between groups

Outcome	Adjusted Mean (se) change within groups				Adjusted Mean (se) change between groups	
	12 weeks – Baseline		24 weeks – Baseline		12 weeks – Baseline	24 weeks – Baseline
	Intervention Group	Control Group	Intervention Group	Control Group	(Intervention – Control)	(Intervention – Control)
Primary Outcome						
MVPA (min/day)						
Secondary Outcomes						
Light Intensity Physical Activity						
Steps/day						

<sup>16 MVPA: Moderate to Vigorous Intensity Physical ActivitySAP version 1.2: Delaware PEAK3/1/24Page 32 of 38

Supplemental table 5: Safety Analyses

Participants n/N (%)	Intervention Group	Control Group
Discontinued participation because of adverse events		
Serious Adverse Event (related or unrelated)		
Hospitalizations (related)		
Hospitalizations (unrelated)		
Deaths (related)		
Deaths (unrelated)		
Nonserious Adverse Event (related or unrelated)		
Back (related)		
Back (unrelated)		
Hip/Thigh (related)		
Hip/Thigh (unrelated)		
Knee (related)		
Knee (unrelated)		
Ankle/Foot (related)		
Ankle/Foot (unrelated)		
Other (related)		
Other (unrelated)		

Supplemental table 6: Comparison of included study participants with valid MVPA data (n=) vs those excluded from this analysis (n=)

Characteristic [mean (sd) or n (%)]	Study Participants	Study participants
	with valid MVPA data (n=)	excluded from MVPA analysis (n=)
	· · · ·	
Age (years mean (sd))		
Weight (kg mean (sd))		
Height (m mean (sd))		
Body Mass Index (kg/m  mean (sd))		
Gender (n (%))		
Women		
Men		

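### Adverse events are actively collected by different people through different contacts in the two arms, so the side-by-side percentages for non-serious events are confounded with ascertainment

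*SAP*

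**What the plan says.** The adverse-event paragraph of SAP section 6.4 gives each arm its own active route. In the intervention arm, events are collected "by the treating physical therapist at the beginning of each session in the intervention". In the control arm they are collected "by a Research Assistant during follow-up reminder phone calls in the Control". The one route that both arms share is passive: "or by spontaneous report on the part of the participant". Protocol section 6.4 describes the same arrangement under the earlier arm names.

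On blinding, SAP section 6.3 states: "The treating physical therapist will not be blinded to group assignment, as they are delivering the Intervention".

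On timing, SAP Table 1 has a single "Adverse Events" row, not split by arm, marked at weeks 0, 1, 2, 4, 7, 10, 12 and 24. The intervention and control rows are both marked at weeks 1, 2, 4, 7 and 10. Table 6 confirms a maximum of five sessions: "Number of physical therapy consultations (0-5), mean (SD)".

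On reporting, SAP section 10 gives frequencies and percentages by arm, and lists non-serious events that exceed 5% in either arm. Supplemental table 5 has adjacent intervention and control columns of n/N (%), including the block "Nonserious Adverse Event (related or unrelated)", which is broken down by body region. No test or interval is planned for these figures.

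**The concern.** Non-serious musculoskeletal events are the harms most relevant to an exercise programme, and their recorded frequency depends heavily on who asks and in what setting. Here the asker and the type of contact are tied to the arm. One arm is asked by the clinician delivering the treatment, at a treatment session. The other is asked by a research assistant, on a call made for another purpose. The SAP gives no common script, no count of contacts per arm, no record of the source of each event and no caveat on the table.

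A reader of Supplemental table 5 will compare the two columns even though no test is attached. A difference in knee, hip or back events could come from the programme, from the way people were asked, or from both, and the plan offers no means of telling these apart. The same applies to an apparent absence of difference. Adverse events are not incidental to this trial: Protocol section 5.2 named their number over 12 weeks alongside the secondary endpoints.

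**Working it through.** There is no figure in the plan to reproduce: neither document gives an adverse-event rate, a detection rate or a number of control calls. The check therefore compares the provisions and then illustrates the size under stated assumptions.

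**Comparison of the provisions**

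| | Intervention | Control |
|---|---|---|
| Active asker (section 6.4) | treating therapist, unblinded | research assistant |
| Contact (section 6.4) | start of each session | follow-up reminder call |
| Number and timing of contacts (section 6.4) | per session; Table 1 marks weeks 1, 2, 4, 7, 10 | not stated |
| Weeks 12 and 24 | marked in Table 1; no active route named in section 6.4 | marked in Table 1; calls possible, timing not stated |
| Passive route | spontaneous report | spontaneous report |

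The difference in asker and contact is stated outright. A difference in frequency is not.

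**Inputs for the illustration**
- From the documents: 100 randomised (SAP section 7); up to five sessions (Tables 1 and 6); the 5% listing threshold (section 10).
- Assumed: 50 per arm (the allocation ratio is not stated), equal true risk in both arms, and the detection probabilities, enquiry yields and call counts below.

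**Who asks.** Observed proportion = true risk × detection probability. Fix detection at 0.9 in the intervention arm. The spurious risk ratio is then 0.9/0.7 = 1.29, 0.9/0.5 = 1.80 or 0.9/0.3 = 3.00, depending on detection in controls. At a true risk of 20%, the table would show 0.20 × 0.9 = 18% against 14%, 10% or 6%. If detection were better in controls, the ratios would invert.

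**Listing rule.** Exceeding 5% of 50 (that is, 2.5) takes at least 3 participants. At a true risk of 10%, the observed rate is 9% in the intervention arm and 7%, 5% or 3% in controls. The binomial chance of 3 or more out of 50 is 84% in the intervention arm, against 69%, 46% or 19% in controls. The arm with poorer detection is thus less likely to bring an event type into the listing.

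**How often.** With q the chance that one enquiry yields a reported event, and k enquiries, the chance of at least one reported event is 1 − (1 − q)^k.
- q = 0.05: five enquiries give 1 − 0.95^5 = 22.6%. One, two, three and five control enquiries give 5.0%, 9.8%, 14.3% and 22.6% (ratios 4.5, 2.3, 1.6 and 1.0).
- Five against two enquiries at q = 0.03: 14.1% against 5.9% (ratio 2.4). At q = 0.10: 41.0% against 19.0% (ratio 2.2).

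This component is exactly zero if control calls were made at the same weeks as the sessions. The formula also gives every enquiry the same yield, whatever interval it covers. That overstates the gap if a later call recovers events from a longer period.

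**After the fix.** With the same question, mode and schedule in both arms, and detection therefore equal, the ratio is 1.0 in every scenario above.

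**The case against.** The best defence is that section 6.4 and Table 1 can be read together: the table says when and the text says who. Table 1 has one adverse-event row for both arms, so nothing shows that controls are asked less often. Silence about call timing does not contradict a schedule that states the weeks. This stands. A reader might infer that controls were asked less often, that the text contradicts the table, or that intervention participants were not asked after week 10. The documents support none of these. The two-call figure above is an assumption, and for weeks 12 and 24 the text only omits to name an asker.

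It also stands that safety reporting is descriptive, that deaths and hospitalisations have their own rows and are less sensitive to who asks, and that related and unrelated events are separated. VAS pain and KOOS are collected identically in both arms at baseline, 12 and 24 weeks, which gives a partial symmetric check on worsening of the knee. It does not cover hip, back or ankle events.

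None of this removes the stated difference in asker and setting. Even with perfectly matched weeks, an unblinded clinician at a treatment session and a research assistant on a reminder call are different instruments, and nothing in either document offsets that.

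**Conclusion.** The point holds for non-serious events. The plan builds a different active collection route into each arm and then sets the arm percentages side by side with no common instrument, source breakdown or caveat. Those percentages and the 5% listing rule are therefore confounded with ascertainment.

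How large the distortion is, and which arm it favours, cannot be derived from the documents. The ratios of 1.29 to 3.00 (who asks) and 1.0 to 4.5 (how often, q = 0.05) are illustrations that rest on equal true risk and the assumed inputs; they are not estimates for this trial. A reader might go further and conclude that the table will show a false excess in the intervention arm, or that the whole safety comparison is invalid. Neither follows: the direction is open, and serious events are much less exposed. The point is worth acting on because the remedy is cheap and bears directly on what the trial can say about harms.

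**What to change.** Which change applies depends on whether collection is still open. The documents do not say; the anticipated recruitment schedule ends in December 2022 and the SAP is dated 2024, so it has probably closed.

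- **If open:** add one identical adverse-event item to the 12- and 24-week online questionnaires in both arms, and base the between-arm comparison of non-serious events on it.
- **If closed:** in Supplemental table 5, tabulate events by source (session, call, spontaneous) and give the number of adverse-event contacts per arm. Limit comparative statements to serious events and to any contacts made in the same way in both arms. Footnote the remaining percentages as not comparable between arms.
- **In either case:** reconcile the adverse-event paragraph of section 6.4 with Table 1. State the number and timing of the control calls, and who asked intervention participants at weeks 12 and 24.

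The cost is one survey item, or extra columns and a footnote, plus a few lines of SAP text. Tabulation by source is possible only where the source was recorded. The comparative table will hold fewer events. If no contacts were made in the same way in both arms, it will hold serious events only. A questionnaire item also relies on recall over 12 weeks.
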